3.2 Randomisation and Blinding

Not applicable (NA).

3.3 Study Treatments and Assessments

Prior to Amendment 6 of the protocol, all patients were dosed with 120 µg/kg/day for 72 weeks. As of Amendment 6, patients enrolled in Cohort 2 received 40 µg/kg/day for at least the first 12 weeks with the option to increase the dose to 120 µg/kg/day for the remaining 60 weeks if there was no improvement in pruritus based on investigator judgement. Patients not tolerating the 120 µg/kg/day dose after a minimum of 1 week for reasons other than new liver findings and severe diarrhoea had the option to down-titrate to a lower dose (40 µg/kg/day). They were to return to the higher dose as soon as deemed appropriate by the Investigator. More than one upward dose titration (from 40 µg/kg/day directly to 120 µg/kg/day) for the same event was not recommended. If, in the opinion of the Investigator, a dose titration should be considered prior to the 1-week minimum, the Investigator was to consult with the Medical Monitor or designee. Any dose titration should have been done in consultation with the Sponsor Medical Monitor or designee.

Study drug was to be dispensed to the patient at defined intervals from Visit 1 through Visit 9, together with instructions on how to store and take the drug. Study drug administration data, including whether each patient took each dose or partial doses of study drug, whether there were any delayed or missed doses, and whether the capsule was opened or swallowed whole, was to be documented through the diaries and transferred to the study database.

Patients participating in the optional extension period were to continue at the same dose as at the end of the 72-week treatment period (120 µg/kg/day or 40 µg/kg/day). Patients not tolerating the dose at any time throughout the extension period were to have the option to down-titrate to a lower dose (40 µg/kg/day) following consultation with the Sponsor Medical Monitor or designee. Patients were to return to the higher dose as soon as deemed appropriate by the Investigator. More than one upward dose titration (from 40 µg/kg/day directly to 120 µg/kg/day) for the same event was not recommended.

Bottles with 34 capsules were to be given to the patient at each visit. A patient who required 2 or more capsules per day was to be given multiple bottles; please refer to the investigational product manual. If a patient's weight changed at any time during the study, dose adjustment was required. The number of capsules provided to the patient was to be based on the body weight thresholds identified in Protocol A4250-008, Table 3.

Odevixibat was to be taken in the morning together with food. On clinic visits days when laboratory assessments were conducted (Visits 1 to 10; and every 16 weeks thereafter for those participating in the optional extension period), study drug was to be taken after the visit.

Efficacy assessments and daily recording of pruritus using an eDiary in this study are briefly introduced as follows.

3.3.1 Serum Bile Acids

Blood samples for analysis of fasting total serum bile acids were to be drawn at all visits from Visit 1 (Visit S-1 for Cohort 2) through Visit 12. Fasting serum bile acids were also to be drawn at all visits (every 16 weeks) during the optional extension period. Patients were to fast (water intake only) for at least 4 hours prior to the collection of samples for serum bile acids. Exceptions could be made for infants <12 months of age if unable to fast for the full 4 hours. For any visit at which a bile acid sample result was unreportable, an additional unscheduled visit for a repeat sample collection may have been scheduled. Samples were to be handled and transported to a central laboratory per instructions in the laboratory manual.

3.3.2 Itching, Scratching, and Sleep Score

Itching, observed scratching, and sleep disturbance were to be recorded twice each day via the eDiary. Patient and/or caregivers were instructed to fill in the eDiary every morning (AM score representing nighttime itching/scratching and sleep disturbance) and evening (PM score representing daytime itching/scratching and tiredness) for the first 24 weeks and the last 21 days before all the remaining visits to the clinic. There was to be no interruption between Visits 11 and 12. Patients participating in the optional extension period stopped eDiary entries at Visit 11. Patients and/or caregivers were instructed to complete the eDiary in the morning after the patient awakened and in the evening just before the patient went to sleep.

The eDiary includes Albireo ObsRO and PRO items. Patients <8 years of age were not asked to complete the Albireo PRO items; the Albireo ObsRO was to be completed by caregivers of patients in this age group. Older patients, ≥ 8 years of age, completed the Albireo PRO items and the caregiver completed the Albireo ObsRO items. The Albireo PRO items assess severity of itch, aspects of sleep disturbance (morning diary only), and tiredness. For patients 8 to 12 years of age, the caregiver read the Albireo PRO items along with the child and recorded the child's response. A guide was provided to the caregivers that provided standardised explanations of the Albireo PRO items, in case the patient was confused or required clarification about the meaning of a question. The Albireo ObsRO items assess severity of observed scratching, aspects of observed sleep disturbance (morning diary only), and observed signs of tiredness (evening diary only). The Albireo ObsRO and PRO scratching and itch severity items use 0 to 4 response scales, where each response is distinguished by a unique facial expression, verbal anchor, number, and colour code.

3.3.3 Growth

Prior to Amendment 6 of the protocol, standard height measurements were obtained, and weight was evaluated using a certified weight scale. As of Amendment 6, growth (height and weight) was to be measured by the standardized assessments outlined in the US FDA guidance document, Orally Inhaled and Intranasal Corticosteroids: Evaluation of the Effects on Growth in Children (March 2007). Height and length (velocity) was to be

measured using a certified stadiometer and weight (Z-score) using a certified weight scale.

Mid-arm circumference (3 repeat measurements) was to be collected at the study site for all patients after Protocol Amendment 6.

Study sites were trained on using a standardized approach when measuring height with a stadiometer and additional detailed instructions were provided in study documents.

BMI was calculated by weight (kg) / height (m)². Change was defined as linear growth deficit (weight and BMI for age) compared to a standard growth curve.

3.3.4 Biomarker Sample

Blood samples for plasma 7 α -hydroxy-4-cholesten-3-one concentration (p-C4) and autotaxin were to be drawn at Visits 1, 2, 5, 8, and 11 for patients with body weight >10 kg. Samples were to be handled and transported to a central laboratory per instructions in the laboratory manual.

3.3.5 Change of Antipruritic Medication

Any change of antipruritic medication must be noted in the eCRF.

3.3.6 Quality of Life Questionnaire (PedsQL)

Patients and caregivers were asked to complete a quality of life (QoL) questionnaire, the Pediatric Quality of Life Inventory (PedsQL), at Visits 1, 5, 8, 11 and at all visits of the optional extension period. Details of the questions included on the questionnaire are located in Appendix 4 of the protocol.

3.3.7 PELD/MELD Score

The paediatric end-stage liver disease (PELD) score was calculated for children under 12 years of age. For children 12 years of age or older, the model for end-stage liver disease (MELD) score was calculated.

For calculation of the PELD/MELD score³ laboratory parameters will be converted in following units:

- Total bilirubin in mg/dL
- Albumin in g/dL
- Creatinine in mg/dL

PELD score = $4.80 * \ln(\text{total bilirubin}) + 18.57 * \ln(\text{INR}) - 6.87 * \ln(\text{albumin}) + 4.36$ (if patient <1 year: scores for patients listed for liver transplantation before the patient's first birthday continue to include the value assigned for age (<1 year) until the patient reaches the age of 24 months) + 6.67 (if the patient has growth failure [< -2 StdDev])

Laboratory values <1.0 were set to 1.0 for the calculation of the PELD score.

MELD score = $9.57 * \ln(\text{creatinine}) + 3.78 * \ln(\text{total bilirubin}) + 11.2 * \ln(\text{INR}) + 6.43$

Laboratory values <1.0 were set to 1.0 and serum creatinine values >4.0 mg/dL (equivalent of 353.6 µmol/L) were set to 4.0 for calculation of the MELD score.

If a patient went from 11 years of age to 12 between the beginning and end of study, both PELD and MELD scores were to be calculated at the first visit after the 12th birthday and move to MELD score.

3.3.8 Fibroscan®

Where available, Fibroscan® was to be performed as per institution standard practice at Visits 1, 5, 8, and 11. The data collected on the Fibroscan form (liver stiffness measured in kPa and controlled attenuation parameter (CAP) measured in dB/m) was to be

³ https://www.unos.org/wp-content/uploads/unos/MELD_PELD_Calculator_Documentation.pdf; accessed on 25-Jul-2018.

converted to determine stage of fibrosis and grade of steatosis, respectively, using a score card^{4,5} as outlined in Table 1 and Table 2.

Table 1: Fibroscan Scoring for Cholestatic Liver Disease (Fibrosis Score)

SCORE	F0 TO F1 NO SCARRING/ MILD FIBROSIS	F2 MODERATE FIBROSIS	F3 SEVERE FIBROSIS	F4 CIRRHOSIS OR ADVANCED FIBROSIS
Fibroscan result	2 to 7 kPa	>7 to 9 kPa	>9 to 17 kPa	>17 kPa

Table 2: Controlled Attenuation Parameter Score and Steatosis Grading

CONTROLLED ATTENUATION PARAMETER SCORE	AMOUNT OF LIVER WITH FATTY CHANGE	STEATOSIS GRADE
<238 dB/m	—	S0
238 to 260 dB/m	11% to 33%	S1
260 to 290 dB/m	34% to 66%	S2
>290 dB/m	≥67%	S3

3.3.9 Markers of Fibrosis

Aspartate aminotransferase to platelet ratio index (APRI) score and fibrosis-4 (Fib-4) score were calculated at Visits 1, 3, 5, 8, and 11.

APRI = [(AST in U/L)/(AST upper limited of normal (ULN) in U/L)] × 100/(platelets in $10^9/L$)

Fib-4 score = (age*AST in U/L)/(platelets in $10^9/L * \sqrt{ALT}$ in U/L)).

3.3.10 Liver Biopsy

If a liver biopsy was performed according to the local regulations or standard of care at any time during Study A4250-008, the biopsy results should have been recorded in the

⁴ Understanding your Fibroscan Results. Memorial Sloan-Kettering Cancer Center Web site. <https://www.mskcc.org/cancer-care/patient-education/understanding-your-fibroscan-results> Updated February 27, 2018. Accessed March 27, 2020.

⁵ Jewish Hospital Fibroscan Interpretation Assessment SOP. Washington University, Louisville Kentucky. <https://louisville.edu/medicine/departments/medicine/divisions/gimedicine/physician-resources/calculators-and-tools-files/fibroscan-interpretation-sheet>. Undated.

eCRF. If the patient had liver biopsy results collected in Study A4250-005 or prior to Week 24 in Study A4250-008, the patient was to be asked to consent to a follow-up liver biopsy, if allowed per local regulations, at Visit 11 unless 2 prior liver biopsy results had been collected with at least one year between biopsies. Liver biopsies were not performed in Spain.

3.3.11 Global Impression of Change and Global Impression of Symptom Measures

Patients, caregivers, and clinicians were to complete the global impression of change (GIC) and the global impression of symptom (GIS) measures at Visits 1, 2, 3, 5, 8, and 11, and at all visits during the optional extension period.

The GIC items assess change in itch (patient version), scratching (caregiver and clinician versions), and sleep (all versions) since starting the study drug. The GIS items assess itch (patient version), scratching (caregiver and clinician versions), and sleep (all versions) in the past week. Caregivers and clinicians were to complete the GIC and GIS for all patients; only patients ≥ 8 years of age were to complete the patient version.

A detailed description of procedures and assessments to be conducted during this study is summarised in the Table 1 Schedule of Assessments (Screening Period through Follow-up Period) and Table 2 schedule of study assessments (Optional Extension Period) of the protocol.

4. Study Endpoints

4.1 Primary Efficacy Endpoints

The primary efficacy endpoints are as follows:

- **EU and Rest of the World (RoW):** Change from baseline in fasting serum bile acids after 72 weeks of treatment.

Change from baseline will be calculated based on the average of the values at Weeks 70 and 72. The baseline fasting serum bile acids value is defined as follows unless otherwise specified:

Cohort 1: The average of the last 2 values before the first dose of study drug in Study A4250-008. In general, these 2 values are the values of the last 2 assessments of Study A4250-005. If pre-dose assessments are collected in Study A4250-008 for a patient, then the values of pre-dose assessments in Study A4250-008 will be considered first and used to calculate the baseline. These 2 values need to be taken from 2 consecutive scheduled visits or unscheduled visits. If only one value is available from 2 consecutive scheduled visits or unscheduled visits, then that value will be used as baseline.

Cohort 2: The average of the last 2 values before the first dose of study drug in Study A4250-008.

- **United States (US):** Proportion of positive pruritus assessments at the patient level over the 72-week treatment period using the Albireo ObsRO instrument. A positive pruritus assessment is defined as a scratching score of ≤ 1 or at least a one-point decrease from baseline on the Albireo ObsRO instrument. At each assessment, the AM score will be compared to the baseline AM average, and the PM score will be compared to the baseline PM average. Both AM and PM pruritus assessments will be included in the analysis of this endpoint. AM scores from the period of 14 days before or on the first dose day in Study A4250-008 will be averaged as the AM baseline. PM scores from the period of 14 days before the first dose day in Study A4250-008 will be averaged as the PM baseline. If a patient's baseline average score is ≤ 1 , then only the criterion of a one-point drop from baseline on the Albireo ObsRO instrument will be used to determine whether a pruritus assessment is positive or not for the primary endpoint analysis.

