2.1 Primary Objectives

Cohort 1

To demonstrate a sustained effect of odevixibat (A4250) on serum bile acids and pruritus in children with progressive familial intrahepatic cholestasis (PFIC) Types 1 and 2.

Cohort 2

To evaluate the effect of odevixibat on serum bile acids and pruritus in patients with PFIC who either (1) Do not meet eligibility criteria for Study A4250-005 (PEDFIC 1) or (2) Patients who do meet the eligibility criteria for Study A4250-005 after recruitment of Study A4250-005 has been completed.

¹ ICH Topic E3: Structure and Content of Clinical Study Reports (CPMP/ICH/137/95- adopted December 1995)

² ICH Topic E9: Statistical Principles for Clinical Trials (CPMP/ICH/363/96 – adopted March 1998).

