- Visit 11: Week 72/optional extension period
- Visit 12: Follow-up visit; Week 76 (for those not participating in optional extension period)
- Optional extension period visits every 16 weeks; Week 88 and onwards

Figure 1 Study Design

[figure not shown]

QD: once daily; T: telephone contact; V: study visit; VS: Visit Screening

Note: Visit 1 coincides with Visit 9 of Study A4250-005. Patients who are not tolerating the 120 µg/kg/day dose may be down-titrated to the 40 µg/kg/day dose following a minimum of 1 week of treatment. The patient can return to the higher dose as soon as deemed appropriate.

This figure is only applicable to Cohort 2 up to Protocol Amendment 5. [Figure 2](#) presents the study design for Cohort 2 as of Protocol Amendment 6.

Figure 2 Study Design for Cohort 2 as of Protocol Amendment 6

QD: once daily; T: telephone contact; V: study visit; VS: Visit Screening

Note: As of Protocol Amendment 6, patients entering Cohort 2 will start treatment at 40 µg/kg/day with the possibility to dose escalate to 120 µg/kg/day after 12 weeks if there is no improvement in pruritus based on investigator judgment. The patient can return to the lower dose if the 120 µg/kg/day dose is not tolerated following a minimum of 1 week of treatment.

Patients were to return to the clinic at Weeks 4 and 12 and thereafter every 10 to 12 weeks for follow-up measurements. Between clinic visits there was to be a telephone contact with the patient and/or caregiver to report AEs. Additional clinic visits may have been required for patients who needed direct site assistance for AE monitoring for safety maintenance and other assessments.

At Visit 11, patients were to be offered the choice to continue receiving odevixibat treatment in an optional extension period. During the optional extension period the patient was to receive odevixibat at the same dose as at the end of the 72-week treatment

period, returning to the clinic every 16 weeks until the drug is commercially available, provided continued use was supported by the risk-benefit profile and the patient had not been previously withdrawn or discontinued from study.

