9.6.3 Analyses of Primary Efficacy Endpoints

All the primary analyses will be based on the FAS, unless otherwise specified.

For the EU and RoW, change from baseline 2 in fasting serum bile acids will be analysed by using the 1-sample t-test or the Wilcoxon signed rank test, as appropriate at the end of the 72-week treatment period based on the average of the values at Weeks 70 and 72. Baseline 2, defined in the table of derived variables in [Appendix A](#), will be used to calculate change from baseline for the summary.

For Cohort 1 patients who were on odevixibat in Study A4250-005, change from Baseline 1 to end of the 72-week treatment in Study A4250-008 will be analysed by using the 1-sample t-test or the Wilcoxon signed rank test, as appropriate. Baseline 1,

defined in the table of derived variables in [Appendix A](#), will be used for this statistical analysis.

For the US, the proportion of positive pruritus assessments at the patient level over the 72-week treatment period using the Albireo ObsRO instrument will be summarised descriptively. A positive pruritus assessment is defined as a scratching score of ≤ 1 or at least a 1-point drop from baseline on the Albireo ObsRO instrument. At each assessment, the AM score will be compared to the baseline AM average, and the PM score will be compared to the baseline PM average. Both AM and PM pruritus assessments will be included in the analysis of this endpoint. For analysis purposes, diary entries will be assigned to a study day based on the recorded date regardless of recorded time. AM scores from the period of 14 days before or on the first dose day in Study A4250-008 will be averaged as AM baseline. PM scores from the period of 14 days before the first dose day in Study A4250-008 will be averaged as PM baseline. If a patient's baseline score is ≤ 1 , then only the criterion of a one-point drop from baseline on the Albireo ObsRO instrument will be used to determine whether a pruritus assessment is positive or not for the primary endpoint analysis. Rounded baseline score will be used for the analysis.

A 95% CI will be provided for the proportion of positive pruritus assessments.

Change from Baseline 1 and 2 in monthly scratching severity score to end of the 72-week treatment in Study A4250-008 will be analysed by using the 1-sample t-test or the Wilcoxon signed rank test, as appropriate. Baseline 1 will only be used for patients in Cohort 1 who were on odevixibat in Study A4250-005.

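### For odevixibat/odevixibat patients entering at a scratching score of 1 or below, the US primary pruritus endpoint does not credit maintained control, and no Baseline 1 version is planned

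*SAP*

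**What the plan says.** For Cohort 1 the primary objective (SAP 2.1) is "To demonstrate a sustained effect of odevixibat (A4250) on serum bile acids and pruritus in children" with PFIC types 1 and 2.

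The US primary endpoint (4.1, repeated in 9.6.3) is each patient's proportion of positive ObsRO scratching assessments over 72 weeks. An assessment is positive if the score is 1 or lower, "or at least a one-point decrease from baseline on the Albireo ObsRO instrument". The AM baseline uses scores from "14 days before or on the first dose day in Study A4250-008 will be averaged as the AM baseline"; the PM baseline is analogous. When the baseline average is 1 or lower, "then only the criterion of a one-point drop from baseline on the Albireo ObsRO instrument will be used". Section 9.6.3 adds: "Rounded baseline score will be used for the analysis". It gives no rounding unit.

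Three other places matter:

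- **Timing (3.1).** "Visit 1 coincides with Visit 9 of Study A4250-005", the end-of-treatment visit of the earlier study.
- **Scale (3.3.2).** The "scratching and itch severity items use 0 to 4 response scales".
- **Baselines (Appendix A).** Baseline 1 precedes the first A4250-005 dose and Baseline 2 precedes the first A4250-008 dose. Baseline 2 is the default. For the monthly scratching score, 9.6.3 plans both and limits the earlier one: "Baseline 1 will only be used for patients in Cohort 1 who were on odevixibat in Study A4250-005". Serum bile acids (9.6.3), growth and pruritus responders (both 9.6.4) also have a Baseline 1 analysis. The proportion of positive assessments does not.

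**The concern.** For a patient who took odevixibat in A4250-005 and rolled over directly, the 14 days before Visit 1 are days on drug. The endpoint then measures further improvement beyond the response already reached, whereas the objective asks whether that response is held. The effect is sharpest in the patients who did best. At a baseline of 1 or lower they lose the criterion that would have credited continued low scores, and the scale leaves little or no room for another one-point fall.

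At stake are the odevixibat/odevixibat column of a primary endpoint and the Odevixibat Overall column, which pools these patients with placebo/odevixibat and Cohort 2 patients whose baselines precede any odevixibat. The on-treatment baseline also reaches the EU/RoW secondary endpoint (4.2), the interval and cumulative proportions, which 9.6.4 summarises in the manner of the US primary analysis, and the subgroup summaries of the primary endpoints (9.8.1).

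**Working it through.** The SAP gives no expected value for this endpoint. Its only power figure (Section 5) concerns surgery, transplantation or death and does not bear on this point. The check is to apply the scoring rule to stable patients.

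**Inputs.** Scores are 0 to 4 (3.3.2). Table 10 expects 280 diary days for Weeks 0–72, so 280 × 2 = 560 planned AM and PM assessments. With baseline B and score s:

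- B > 1: positive if s ≤ 1 or B − s ≥ 1.
- B ≤ 1: positive only if B − s ≥ 1, that is, s ≤ B − 1.

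**Constant scores.**

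- B = 0, s = 0 throughout: needs s ≤ −1, which is impossible. 0 of 560, 0%.
- B = 1, s = 1 throughout: needs s = 0. 0 of 560, 0%.
- Any unrounded B < 1: B − 1 is negative, so 0% whatever follows.

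**Stable mix of 0s and 1s with mean m.** Rounding to an integer (half up) is assumed, since the unit is not stated. If m < 0.5, B rounds to 0 and the result is 0%. If 0.5 ≤ m ≤ 1, B rounds to 1 and only zeros count, so the result is 1 − m. If B is left unrounded, any mix with m < 1 gives 0%.

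| m | B rounded | B unrounded |
|---|---|---|
| 0.5 | 50% | 0% |
| 0.6 | 40% | 0% |
| 0.8 | 20% | 0% |
| 0.95 | 5% | 0% |
| 1.0 | 0% | 0% |

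**Stable mix of 1s and 2s.** Above 1 the ≤1 criterion stays on and the 1s count. It matters, though, whether the switch-off looks at the rounded value, because means of 1.2 and 1.4 round to 1.

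| Mean | Switch-off on unrounded B | Switch-off on rounded B |
|---|---|---|
| 1.2 | 80% | 0% |
| 1.4 | 60% | 0% |
| 1.6 | 40% | 40% |
| 1.8 | 20% | 20% |

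**Constant 2.** B = 2 keeps the ≤1 criterion, but 2 is above 1 and 2 − 2 = 0, so the result is 0%. A patient who fell from 4 to 2 in A4250-005 and held there is in this position. The cause is the on-treatment baseline; the switch-off plays no part.

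**Same patients against Baseline 1.** Take Baseline 1 = 3 for illustration. Constant 0 and constant 1 are positive on either criterion. Constant 2 is positive because 3 − 2 = 1. All three score 100%.

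**Effect on the group mean.** Suppose a share f of the group enters at 1 or lower, holds there, and scores 0% where a pre-odevixibat baseline would give 100%. The group mean is then lower by 100 × f percentage points: 20 at f = 20%, 50 at f = 50%. The SAP does not give f, so these values are assumptions. The result is also a ceiling, because mixed 0/1 patients can keep part of their credit.

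**The case against.** The switch-off has an evident purpose: without it, a patient entering at 1 or lower and not changing would score 100% positive with no change from study baseline. Study entry is also the SAP's declared default baseline. There is no formal hypothesis testing (Section 5), the endpoint is summarised descriptively with a confidence interval, the affected group has its own column (9.1), and the error runs towards no effect, so it cannot produce a false claim of benefit. All of this stands and limits the consequence. It does not make the endpoint measure maintenance.

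Some stronger readings go further than the document supports:

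- *The ≤1 criterion is off for all Cohort 1 patients already on odevixibat.* It is not. Section 4.1 makes this conditional on a baseline of 1 or lower.
- *Every sustained response scores 0%.* With an integer-rounded baseline, a stable 0/1 mix averaging 0.5 or more but below 1 scores above 0%.
- *Maintenance of the pruritus effect is not assessed at all.* Section 9.6.3 plans change from Baseline 1 in the monthly scratching score, and 9.6.4 a Baseline 1 responder analysis with a 1.0-point threshold. A patient who fell from 3 to 0 and stayed there is a responder.
- *The primary definition should be replaced.* The study is open-label, with interim efficacy analyses at the July 2020 and July 2022 data cuts (Section 6). Replacing the baseline now, in the direction that raises the active group's result, would be open to challenge.
- *The bile acid endpoint has the same gap.* A Baseline 1 bile acid analysis is already planned for this group.

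**Conclusion.** The point holds for Cohort 1 patients who rolled over directly from odevixibat with an on-treatment baseline of 1 or lower. For them, constant control at 0 or 1 scores 0%, any unrounded baseline below 1 scores 0% whatever follows, and under integer rounding a stable 0/1 mix averaging 0.5 to 1 scores between 50% and 0%. Patients who improved in A4250-005 and hold at 2 also score 0%, because of the baseline alone. Patients who enrolled after a dosing gap (9.1) may have an off-treatment baseline and are outside this conclusion.

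The result conflicts with the sustained-effect objective, biases the odevixibat/odevixibat column towards no effect, and makes Odevixibat Overall hard to interpret. The planned Baseline 1 analyses inform on maintenance but do not repair this endpoint. The size at group level cannot be fixed from the SAP, because the number of such patients is not given. Results for baselines from 0.5 up to just below 1.5 also depend on a rounding rule that the SAP leaves open.

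**What to change.** In Section 9.6.3:

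1. For odevixibat/odevixibat patients, add a version of the proportion of positive assessments scored against the Baseline 1 AM and PM averages (14 days before the first A4250-005 dose), specified before database lock. Report it beside the planned Baseline 2 version, and label the latter as showing further improvement only.
2. For this endpoint, add an Odevixibat Overall summary that uses each patient's last pre-odevixibat baseline: Baseline 1 for odevixibat/odevixibat, Baseline 2 for placebo/odevixibat and Cohort 2.
3. State whether the ≤1 test uses the rounded or the unrounded baseline, and give the rounding unit.

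The cost is SAP wording, one extra derivation and one extra table. The A4250-005 pre-dose diary scores are already needed for the monthly-score and responder analyses. Because the new version comes after interim looks at open-label data, it should be labelled supplementary, and the planned primary definition should stay in place.
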